## **2.4 Study design**

This is a double-blind, placebo-controlled, randomized, multi-center phase-II study. Patients aged between 18 and  $\leq 60$  years with newly diagnosed AML will receive an induction and consolidation chemotherapy together either with Placebo (Arm P; control arm) or with Sorafenib (Arm V; study arm). Patients will additionally receive maintenance therapy with either Placebo (Arm P) or with Sorafenib (Arm V) for one year after the start of maintenance therapy. For further details see chapter 4.3.

### **3 SELECTION, RANDOMIZATION AND WITHDRAWAL OF PATIENTS**

#### **3.1 Patient selection**

According to the sample size calculation given in chapter 7,  $n = 276$  patients will be included in the study with an equal allocation rate to both treatment arms.

##### **3.1.1 Inclusion criteria**

- Patients with newly diagnosed AML (except APL) according to the FAB and WHO classification, including AML evolving from MDS or other hematologic diseases and AML after previous cytotoxic therapy or radiation (secondary AML)
- Bone marrow aspirate or biopsy must contain  $\geq 20\%$  blasts of all nucleated cells or differential blood count must contain  $\geq 20\%$  blasts. In AML FAB M6  $\geq 30\%$  of non-erythroid cells in the bone marrow must be leukemic blasts. In AML defined by cytogenetic aberrations, the proportion of blasts may be  $< 20\%$ .
- Age  $\geq 18$  and  $\leq 60$  years
- Informed consent, personally signed and dated to participate in the study
- ECOG performance status of 0-1
- Life expectancy of at least 12 weeks
- Adequate liver and renal function as assessed by the following laboratory requirements to be conducted within 7 days prior to screening:
  - Total bilirubin  $\leq 1.5$  times the upper limit of normal
  - ALT and AST  $\leq 2.5$  times upper limit of normal
  - Alkaline phosphatase  $< 4$  x upper limit of normal
  - PT-INR/PTT  $< 1.5$  x upper limit of normal (patients who are being therapeutically anticoagulated with an agent such as coumarin or heparin will be allowed to participate provided that no prior evidence of underlying abnormality in these parameters exists).
- Creatinine  $\leq 1.5$  times upper limit of normal

##### **3.1.2 Exclusion criteria**

- Patients who are not eligible for standard chemotherapy as per discretion of the treating physician
- Central nervous system manifestation of AML
- Cardiac disease: heart failure NYHA III or IV; unstable coronary artery disease (MI more than 6 months prior to study entry is permitted); serious cardiac ventricular arrhythmias requiring anti-arrhythmic therapy (beta blockers or digoxin are permitted)

- Chronically impaired renal function (creatinine clearance < 30 ml/min) (Cockcroft-Gault formula)
- Patients undergoing renal dialysis
- Chronic pulmonary disease with relevant hypoxia
- Known HIV and/or hepatitis C infection
- Evidence or history of severe non-leukemia associated bleeding diathesis or coagulopathy
- Evidence or recent history of CNS disease, including primary or metastatic brain tumors, seizure disorders
- Resting blood pressure (BP) consistently higher than systolic 160 mmHg and/or diastolic 95 mmHg
- Any severe concomitant condition which makes it undesirable for the patient to participate in the study or which could jeopardize compliance of the protocol
- Patients with major surgery, open biopsy or significant traumatic injury within 4 weeks of start of first dose
- Serious, non-healing wound, ulcer or bone fracture
- Uncontrolled active infection > Grade 2 NCI-CTC version 3.0
- Concurrent malignancies other than AML
- History of organ allograft
- Allergy to study medication or excipients in study medication
- Pregnant or breast-feeding patients. Women of childbearing potential must have a negative pregnancy test performed within 7 days prior to the start of treatment.
- Previous treatment of AML except hydroxyurea for up to 5 days
- Concomitant or previous treatment with kinase inhibitors, angiogenesis inhibitors or Mylotarg
- Investigational drug therapy outside of this trial during or within 4 weeks of study entry
- Patients unable to swallow oral medications
- Substance abuse, medical, psychological or social conditions that may interfere with the patient's participation in the study or evaluation of the study results

### 3.2 Registration

Eligible patients will be centrally registered by the Studienzentrale SAL after the local center has faxed the patient registration form (Patientenmeldebogen) to [name].

Required details for registration are:

- Individual **patient number (Patientennummer)**
- Age

- Sex
- Diagnosis (according to the FAB-classification)
- Study center and name of the physician

The individual **patient number** will be specific for the local center and be assigned by the local center. **The patient number consists of three digits for the number of the local center and three digits for the individual patient.** The local center shall assign the three patient digits consecutively according to order of inclusion, starting with 001 and counting up, i.e. the first included patient of center XXX will be assigned XXX-001, the following patient will be assigned XXX-002 and so forth. The name or date of birth will not be submitted to the Studienzentrale (see chapter 9.3 Confidentiality).

A form for registration and randomization (Patientenmeldebogen) with all relevant contact information is provided in the Investigator Site File (ISF, Prüfarztordner). After registration by the center and after having obtained the molecular and cytogenetic information from the reference laboratories, the Studienzentrale SAL will perform the randomization of the patients to the two treatment arms in a stratified manner. Since treatment is homogenous in both treatment arms until day 10 randomization will be done latest at day 7. The center will be immediately informed about the randomization result in order to assure study drug supply until day 10.

### **3.3 Randomization Procedure and Stratification**

#### **3.3.1 Randomization**

The Studienzentrale SAL is responsible for the randomization process. The central randomization process will ensure allocation concealment. The randomization will be based on a randomization list containing randomization blocks. The use of randomization blocks guarantees equal numbers of patients in each treatment arm. In order to ensure equal proportions of patients from different strata in the two treatment arms, separate randomization lists for each stratum will be used (for description of strata, see below). Eligible study patients will be randomized by consecutive inclusion in the stratum-specific randomization list according to their cytogenetically or molecular defined stratum. Patients will be assigned one of the two treatment arms according to the randomization list (A or B).

The pharmacy in Dresden (Klinikapotheke des Universitätsklinikums Dresden) will assign treatment arms A or B to individual medication bottle numbers and will send the necessary supply of bottles to each participating center (see chapter 4.1.3, Drug accountability). A copy of the list containing medication numbers per center will be deposited at the Studienzentrale SAL.

Therefore, the Studienzentrale SAL will know which individual medication number corresponds with treatment arm A or B and will accordingly select and assign a medication bottle number to the randomized patient and add this number to the pre-existing patient study number. **The patient number plus the added three digits of the medication number will form the randomization number (Randomisationsnummer).** The Studienzentrale SAL will report the number to the recruiting center by fax. Figure 1 illustrates the general composition of the randomization number.

CCC – PPP – MMM

CCC = three digits for local trial center (Kliniknummer)

PPP = three digits for patient inclusion number

MMM = three digits for medication number

*Figure 1: Composition of the randomization number (Randomisationsnummer)*

In order to ensure double blinding, the pharmacy will assign treatment arm A and B to Sorafenib or Placebo and neither the Studienzentrale SAL nor the investigators will know which treatment arm corresponds to Sorafenib and Placebo, respectively. The closed envelopes concealing the allocation of the individual patients will be deposited at the Dresden pharmacy and the local trial site only and not at the Studienzentrale. The Studienzentrale SAL will keep the randomization lists confidential and will not report the treatment arm to the investigators in order to ensure that in case of unblinding of one patient the investigator remains blinded for all other included and randomized patients. In case of unblinding, the investigators will have to contact the Safety Board which is separated from the randomization department at the Studienzentrale SAL. Even if the investigator reports the result of the unblinding to the Safety board, the results will not be reported to the randomization department. Therefore, in case of unblinding of an individual patient, the randomization department at SAL will still not be able to know which treatment arm corresponds with Placebo or Sorafenib and blinding throughout the whole trial period is guaranteed.

The centers will be supplied with starter medication kits after initiation of the study in the individual center. The center will report the eligible patient to the Studienzentrale SAL by faxing the patient registration form (Patientenmeldebogen) and send the required bone marrow and blood probes (Table 16, page 29) to the central laboratories (Table 17, page 29). After the Studienzentrale SAL has received the molecular and cytogenetic test results from the reference laboratories, the Studienzentrale SAL will perform the randomization as described above and

report the **randomization number** to the trial site via fax response. The number will be noted in the patient file and in the trial documentation forms. **The last three digits of the randomization number correspond with the number of the individual medication bottles available at the trial center.** The patient will then receive the medication bottles labeled with her/his individual **randomization number** (center number plus patient number plus number of individual medication bottle). Since treatment is homogenous in both treatment arms until day 10, randomization will be done latest at day 7. The center will be immediately informed about the randomization result in order to assure study drug supply until day 10.

### 3.3.2 Stratification

Drug assignment will be performed in a balanced way according to the individual patient risk. Cytogenetic risk definition will be done according to Bloomfield et al.. This definition includes:

- **low risk (LR):** t(8;21)(q22;q22) ;inv(16)(p13q22)/t(16;16)(p13;q22)
- **intermediate risk (IR):** normal karyotype, balanced structural rearrangement: t(9;11)(p22;q23), unbalanced structural rearrangements: del(7q), del(9q), del(11q), del(20q), numerical aberrations: -Y, +8, +11, +13, +21 and all other patients who do not fulfil low or high risk criteria
- **high risk (HR):** complex karyotype, balanced structural rearrangement inv(3)(q21q26), t(3;3)(q21;q26), t(6;9)(p23;q34) t(6;11)(q27;q23), t(11;19)(q23;p13.1), unbalanced structural rearrangement: del(5q), numerical aberrations: -5; -7
- additionally **high risk (HR)** criteria will be fulfilled if a blast count  $\geq 10\%$  at the day 16 bone marrow control is evident, however no stratification will be done based on this analysis

On the basis of the known prognostic significance of the Flt3 and NPM status, the IR group will be subdivided into four different strata. This results in six distinct risk strata which will be used for stratification in this trial. The composition of the strata is shown in Table 1.

Since stratification is necessary for a well balanced trial, an urgent definition of molecular markers of the patients will be done. The results of the analysis have to be obtained latest by day 7 of the chemotherapy protocol to ensure drug order until day 10.

Definition of Strata						
S	HR cyto-genetics: yes	HR cyto-genetics: no  LR cyto-genetics: yes	HR cyto-genetics: no  LR cyto-genetics: no  NPM1-Mut: yes  FLT3-Mut: no	HR cyto-genetics: no  LR cyto-genetics: no  NPM1-Mut: yes  FLT3-Mut:yes	HR cyto-genetics: no  LR cyto-genetics: no  NPM1-Mut: no  FLT3-Mut: yes	HR cyto-genetics: no  LR cyto-genetics: no  NPM1-Mut: no  FLT3-Mut: no
1	x					
2		x				
3			x			
4				x		
5					x	
6						x

Table 1: Definition of Strata

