## ABBREVIATIONS

AE	Adverse Event
ALT	Alanine Transaminase
AMG	Arzneimittelgesetz
AML	Acute Myeloid Leukemia
AMLCG	AML Cooperative Group
ANC	Absolute Neutrophil Count
AP	Alkaline Phosphatase
APL	Acute Promyelocytic Leukemia
AR	Adverse Reaction
AraC	Cytosine Arabinoside
AST	Aspartate Transaminase
AT III	Antithrombin III
ATP	Adenosin Triphosphate
AUC	Area Under the Curve
BID	twice daily
BM	Bone Marrow
BP	Blood Pressure
BSA	Body Surface Area
CBC	Complete Blood Count
CFR	Code of Federal regulations
CNS	Central Nervous System
CR	Complete Remission
CRi	Complete Remission with incomplete regeneration of peripheral blood
CRc	Complete Cytogenetic Remission
CRm	Complete Moleculargenetic Remission
CRA	Clinical Research Associate
CrCl	Creatinin Clearance
CRF	Case Report Form
CT	Chemotherapy
CTCAE	Common Toxicity Criteria for Adverse Events
CYP	Cytochrome P
DLT	Dose Limiting Toxicities
DNA	Desoxyribonucleic Acid
DSIL	Deutsche Studieninitiative Leukämie
DSMB	Data Safety Monitoring Board
ECG	Electrocardiogram
ED	Early Death
ECOG	Eastern Cooperative Oncology Group
EDTA	Ethylenediaminetetraacetic acid

EFS	Event Free Survival
FAB	French-American-British Cooperative Group
FDA	Food and Drug Administration
Flt	Fms like Tyrosine Kinase
FISH	Fluorescence In Situ Hybridization
GCP	Good Clinical Practice
G-CSF	Granulocyte Colony Stimulating Factor
GI	Gastrointestinal
GM-CSF	Granulocyte Macrophage Colony Stimulating Factor
HCC	HepatoCellular Cancer
HD-AraC	High Dose-Cytarabine
HFSR	Hand-Foot Skin Reaction
HIV	Human Immunodeficiency Virus
HR	cytogenetically High Risk
ICH	International Conference on Harmonization
INR	International Normalized Ratio
IR	cytogenetically Intermediate Risk
IRB/IEC	Institutional Review Board/ Independent Ethics Committee
ITD	Internal Tandem Duplication
ITT	Intention To Treat analysis
LDH	Lactatedehydrogenase
LKP	Leiter der Klinischen Prüfung
LR	cytogenetically Low Risk
MAPK	mitogen-activated protein kinase
MDS	Myelodysplastic Syndrome
mg	miligram
MI	Myocardial Infarction
mm	millimeter
MRD	Minimal Residual Disease
NCI-CTC	National Cancer Institute Common Toxicity Criteria
nM	nanoMol
NPM	Nucleophosmin
OS	Overall Survival
PB	Peripheral Blood
PDGF	Platelet-Derived Growth Factor
PDGFR	Platelet-Derived Growth Factor Receptor
PE	Physical Examination
PK	Pharmacokinetic
p.o.	per os = per mouth
PR	Partial Response
PT-INR	Prothrombin Time-International Normalized Ratio

PTT	Partial Thromboplastin Time
QOD	Once Every Other Day
QD	Once Every Day
RNA	Ribonucleic Acid

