### 4.3.3 Consolidation therapy

#### 4.3.3.1 Consolidation therapy for LR patients as defined by cytogenetics and for IR patients without an HLA-identical sibling

All patients in CR/ CRi after induction therapy should receive three courses of HD-AraC consolidation therapy not earlier than one week after attaining CR/ CRi. If, in the opinion of the treating physician, the patient's condition does not allow for consolidation therapy, consolidation therapy can be postponed for up to 4 weeks after a CR/ CRi is reached. However, if the patient is not attaining CR/ CRi 5 weeks after the beginning of the second induction therapy course he/she should be classified as treatment failure (definition of event and EFS see chapter 7) and study treatment should be terminated .

Criteria for the beginning of each consolidation course: platelets > 70.000/μl and neutrophils > 1.000/μl.

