#### **4.3.3.3 Consolidation therapy for HR patients:**

All patients in CR/ CRi after induction therapy should receive a consolidation therapy based on allogeneic stem cell transplantation. This may involve transplantation procedures from either an HLA identical sibling or an unrelated HLA-matched donor. The patients will be censored for outcome analysis at the beginning of conditioning chemotherapy for transplantation and will not receive any further treatment with Sorafenib. If there is no donor availability, patients proceed with treatment as described under 4.3.3.1.

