## 7 STUDY OUTCOME AND STATISTICAL ANALYSIS

### 7.1 Power and Sample Size Calculation, Interim Analysis

Power calculations are based on the following assumptions:

Control group:	median event free survival (EFS) 9 months
Sorafenib group:	median event free survival (EFS) 13.5 months (improvement of 50%)
Error of first kind:	$\alpha = 0.05$ (two sided)
Power:	80%
Accrual time:	24 months
Follow up:	18 months
Randomization:	1/1 allocation

To detect an improvement of median EFS from 9 months to at least 13.5 months, we need 125 evaluable patients per group i.e. a total of 250 patients to yield the necessary number of approximately 191 events.

Although all efforts will be taken to avoid patient loss to follow up, there might be a rate of loss due to various possible reasons. Censoring by transplantation in first remission will lead to an additional loss. The rate of allogeneic transplantation is assumed with about 10% of the patients. Patients receiving allogeneic stem cell transplantation will be censored for analysis at the time point of transplant. In order to account for this, exponential hazard of 0.0074 is incorporated in the sample size calculation.

Within 24 months the participating centers are able to recruit up to 300 patients fulfilling the inclusion and exclusion criteria. Taking into account a drop out rate of about 10 % the study-centers will recruit the necessary number of patients (n=276) within 24 months.

All calculations are done using SAS-Software (PROC POWER) licensed to the University of Münster.

One interim analysis and the final analysis are planned for the intent-to-treat EFS endpoint such that the overall type I error is controlled at a two-sided 0.05 level. Interim analysis will be done according to the O'Brien/Flemming approach. When 50% of the expected intent-to-treat EFS events (191 events  $\times$  0.5 = 95) are attained the first interim analysis on the intent-to-treat EFS endpoint will be conducted.

The (unblinded) interim analysis will be performed by the Studienzentrale SAL in cooperation with Institut für Medizinische Informatik und Biometrie, Münster.

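### Low- and some intermediate-risk patients with day-16 blasts of at least 10% and a donor fall under two consolidation rules that differ on study drug and EFS censoring

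*Protocol*

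**What the plan says.** Section 3.3.2 sorts patients into LR, IR and HR by karyotype. It then adds that the HR "criteria will be fulfilled if a blast count" of at least 10% is found at day 16, with no exception for LR or IR karyotypes, "however no stratification will be done based on this analysis". Its IR group names certain karyotypes, including the normal one, and ends with a residual class: "and all other patients who do not fulfil low or high risk criteria".

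The abbreviation list expands HR as "cytogenetically High Risk" and IR as "cytogenetically Intermediate Risk", with no reference to day 16.

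Three sections set consolidation:

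- 4.3.3.1 is headed "Consolidation therapy for LR patients as defined by cytogenetics and for IR patients without an HLA-identical sibling". Patients in CR/CRi get three HD-AraC courses with study drug, which lead to a year of maintenance (4.3.4).
- 4.3.3.2 sends IR patients with an HLA-identical sibling to transplant. They are censored at the start of conditioning and get no more Sorafenib.
- 4.3.3.3, for HR patients, reads: "All patients in CR/ CR i after induction therapy should receive a consolidation therapy based on allogeneic stem cell transplantation". The donor may be a sibling or a matched unrelated donor. Censoring and the end of Sorafenib are as in 4.3.3.2. Patients without a donor go back to 4.3.3.1.

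Section 7.1 states: "The rate of allogeneic transplantation is assumed with about 10% of the patients".

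**The concern.** The consolidation sections use the risk labels as if each patient had exactly one. The day-16 clause gives some patients a second label, and the text does not say which one governs.

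Take a patient with t(8;21) whose day-16 marrow shows 15% blasts, who later reaches CR and who has a donor. This patient is LR by cytogenetics under 4.3.3.1 and HR under 3.3.2 with 4.3.3.3. On one path study drug continues through consolidation and a year of maintenance, and EFS is followed to an event. On the other, study drug ends and EFS is censored at conditioning.

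Two centres could treat the same patient differently and each cite the protocol. Both the treatment delivered and the censoring of the primary endpoint would then depend on how the centre reads the text. An analysis plan cannot repair this afterwards, because the rule decides what treatment is given.

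**Working it through.** **1. Which patients meet two rules.** All rows assume day-16 blasts of at least 10% and CR/CRi after induction.

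| Cytogenetic group | Donor | Following karyotype | Following the day-16 clause | Result |
|---|---|---|---|---|
| LR | sibling or unrelated | 4.3.3.1: HD-AraC, study drug | 4.3.3.3: transplant, censored, Sorafenib ends | direct clash |
| LR | none | 4.3.3.1 | 4.3.3.3, which returns to 4.3.3.1 | agree |
| IR | HLA-identical sibling | 4.3.3.2: transplant, censored, Sorafenib ends | 4.3.3.3: the same | agree |
| IR | unrelated only | 4.3.3.1 | 4.3.3.3 | ambiguous |
| IR | none | 4.3.3.1 | 4.3.3.3, which returns to 4.3.3.1 | agree |
| HR | any | 4.3.3.3 | 4.3.3.3 | agree |

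The LR row is a clash because 4.3.3.1 ties LR expressly to cytogenetics, while 3.3.2 makes the same patient HR. The IR row is an ambiguity. A normal karyotype is IR by name, but the residual wording and the day-16 clause allow the patient to be moved to HR.

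**2. Whether the day-16 clause can be set aside.** It is not used for stratification. The choice of second induction (4.3.2) uses a different test, whether blasts have fallen. That leaves consolidation as its only visible use. If HR means karyotype alone, the clause does nothing. If it is applied, it contradicts the abbreviation list and the LR wording of 4.3.3.1.

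**3. Treatment time at stake.** Consolidation courses start no earlier than day 28, and maintenance starts on day 8 of the third. The first consolidation day to the start of maintenance is therefore about 2 months at minimum spacing. Adding 12 months of maintenance gives about 14 months for a patient who completes everything.

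**4. The design figures.** Inputs from 7.1 are medians of 9 and 13.5 months, two-sided 0.05, 80% power, 24 months' accrual, 18 months' follow-up and a loss hazard of 0.0074 (taken as per month).

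- Hazard ratio: 9/13.5 = 0.667.
- Events (Schoenfeld): 4 × (1.960 + 0.842)² / (ln 0.667)² = 191, as stated.
- Observed-event probability for event hazard λ, loss hazard γ, L = λ + γ and follow-up u uniform on 18 to 42 months: (λ/L) × mean of (1 − e^(−Lu)). This gives 0.827 for control (λ = ln 2/9) and 0.711 for Sorafenib (λ = ln 2/13.5), mean 0.769.
- N = 191/0.769 = 248, against the stated 250.

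**5. Sensitivity to more transplant censoring.** The hazards above 0.0074 are assumptions.

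| Loss hazard per month | Censored before an event | Events, 250 patients | Power, 250 | Power, 276 |
|---|---|---|---|---|
| 0.0074 | 9% | 192 | 80% | 84% |
| 0.0125 | 15% | 183 | 78% | 82% |
| 0.02 | 22% | 171 | 75% | 79% |
| 0.03 | 30% | 156 | 72% | 76% |

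**6. How many patients.** The documents do not give the inputs. Assume 80–85% without HR cytogenetics, 20–40% of these with day-16 blasts of at least 10%, and 50–60% of those reaching CR/CRi:

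- Low: 0.80 × 0.20 × 0.50 = 0.08, or 22 of 276.
- High: 0.85 × 0.40 × 0.60 = 0.204, or 56 of 276.

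This is an upper envelope, because it ignores donor status and so includes rows where the rules agree. If 35–70% of these patients were in a disputed donor situation (also an assumption), 22 × 0.35 = 8 to 56 × 0.70 = 39 would remain. For scale, 10% of 276 is about 28 planned transplants.

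**The case against.** The best defence is that the text can be read as one rule per patient. The cytogenetic qualifier in the 4.3.3.1 heading attaches only to LR, so LR patients stay in 4.3.3.1 whatever day 16 shows. The residual IR wording removes patients who meet the day-16 criterion, so they become HR. The protocol also writes of HR cytogenetics when it means karyotype alone (2.3.2 and Table 1), while 4.3.3.3 speaks simply of HR patients, and a glossary entry should not override an operative definition. This is a fair reading, and it is why the IR case is only an ambiguity. For LR it requires the 4.3.3.1 heading to override 3.3.2, which the text never says.

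Figure 2, the treatment flow chart, is not reproduced in the copy reviewed and may show the routing. If it does, it would help sites, but the sections would still disagree.

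Three stronger inferences are tempting, and the documents do not support them:

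- **Every LR or IR patient with a high day-16 count is in conflict.** Donor status removes several groups, as the table shows, so 22 to 56 patients is not a count of conflicts.
- **The unclear wording favours one arm.** The day-16 marrow follows the start of study drug on day 10, so the trigger is post-randomization and could differ by arm. A clear day-16 rule would share that property, and sites are blinded.
- **The sample size is wrong.** The figures reproduce, and the 10% transplant rate is stated as an assumption.

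**Conclusion.** The point holds in limited form. For LR patients by cytogenetics with day-16 blasts of at least 10%, CR/CRi and an available donor, 3.3.2 with 4.3.3.3 and 4.3.3.1 cannot both be followed. For IR patients with such a marrow, CR/CRi and only an unrelated donor, the text supports either path. Elsewhere the rules agree.

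For an affected patient the reading decides up to about 14 months of study drug at minimum course spacing, and whether EFS is censored at conditioning. The number of such patients cannot be derived from the protocol; the counts in the working rest wholly on assumptions.

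No design figure is shown to be wrong. The 10% transplant assumption cannot be judged until the rule is settled. The sensitivity table suggests that heavier transplant censoring would cost a moderate amount of power. The main harm is treatment and censoring that can vary by centre. It should be corrected in the protocol.

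**What to change.** Reconcile the abbreviation list, 3.3.2 and 4.3.3.1 to 4.3.3.3, and Figure 2 if needed, so that each combination of cytogenetic group, day-16 result and donor status falls under exactly one consolidation rule. A one-page decision table would do this. Use separate labels for HR by cytogenetics and HR by day-16 blasts throughout. Then confirm that the transplant assumption of about 10% and the loss hazard in 7.1 match the rule chosen, and restate them if they do not. Which rule applies is a clinical decision for the sponsor.

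The cost is protocol wording. The possible downside is a less favourable transplant and censoring assumption, and so somewhat lower power or a larger sample.
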